5.12.8. Patient Narratives

Patient narratives will be provided for all patients in the study who experience any of the following “notable” events prior to data cutoff for the submission:

- deaths
- serious adverse events
- discontinuations from study (or study drug) due to AEs
- pregnancy

A list of patients who meet the criteria for narratives will be provided.

5.13. Subgroup Analyses

5.13.1. Subgroup Analyses for HbA1c

The following subgroups will be analyzed for HbA1c if there are sufficient numbers of patients per group (eg, at least 10% in each group) for both the ITT and efficacy estimands:

- age (age group 1: 1 to <12 versus 12 to <18 years and age group 2: 1 to <6, 6 to <12, and 12 to <18 years)
- Body Mass Index (BMI, < 25 kg/m², ≥ 25 kg/m² and < 30 kg/m², ≥ 30 kg/m²)
- hemoglobin A1c stratum ($\leq 8.0\%$ versus $> 8.0\%$)

- sex (male versus female)
- duration of diabetes (using the median as the cut-off)
- race
- ethnicity
- country
- region
- type of basal insulin (glargine, degludec and detemir)
- prandial insulin dosing plan (carbohydrate counting or pattern adjustment)
- personal continuous glucose monitoring (CGM) or flash glucose monitoring (FGM) use (yes, no)

For the ITT estimand, analyses for HbA1c and change from baseline in HbA1c will be performed using an ANCOVA model that includes the same fixed effects and baseline as a covariate given for the primary analysis model plus factors of subgroup and 2-way interaction of subgroup and treatment.

For the efficacy estimand, analyses for HbA1c and change from baseline in HbA1c will be performed using an MMRM model that includes the same fixed effects given for the primary analysis model plus factors of subgroup, 2-way interaction of subgroup and treatment, 2-way interaction of subgroup and visit, and 3-way interaction of treatment, visit, and subgroup. The interaction of subgroup and treatment at the primary endpoint will be evaluated to assess the treatment by subgroup interaction.

The subgroup interaction effect will be evaluated using a significance level of 0.10, unadjusted.

Additional subgroup analyses may also be performed.

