Review and discuss SMBG (and/or CGM/FGM) and hypoglycemia data from patient study diary				X			X			X		X			X		
Discuss SMBG (and/or CGM/FGM) and hypoglycemia data with patient			X		X	X		X	X		X		X	X			
Review/discuss only severe hypo data after completion of study treatment																X	

	Screen a	Lead-In		Treatment Period												Safety Follow-Up	ED b
eCRF Visit Number	1	2	3 c	4	5 c	6 c	7	8 c	9 c	10	11 c	12	13 c	14 c	15	801 d	ED
Weeks from Randomization	-5	-4	-2	0	2	4	6	8	10	12	15	18	21	24	26	28	
Visit Window (±days)		3	3	3	7	7	7	7	7	7	7	7	7	7	7	7	
Patient returns unused study drug or open-label Humalog supplies				X			X			X		X			X		X
Drug accountability log				X			X			X		X			X		X
Laboratory Assessments																	
Pregnancy test, serum/urine (applicable females only) n	X			X													
Urinalysis (screening)	X																
HbA1c	X			X			X			X					X		X
Clinical chemistry	X														X		X
Hematology	X														X		X
Antilispro antibodies	X			X			X			X					X		X

Abbreviations: DBP = diastolic blood pressure; eCRF = electronic case report form; ED = early discontinuation; HbA1c = hemoglobin A1c; HR = heart rate; IP = investigational product; IWRS = interactive web-response system; SBP = systolic blood pressure; SMBG = self-monitored blood glucose; WHO = World Health Organization.

- a Patients who rescreen will start at Visit 1.
- b Randomized patients who decide to discontinue will be asked to return for the ED visit. If a patient discontinues during an office visit that visit may be treated as the ED visit. If a patient discontinues via telephone, they will be asked to return for the ED visit.
- c Telephone visits are indicated by shaded columns. Telephone visits can become office visits. Site documentation will serve as the source for telephone visits.
- d V801 will be a telephone visit; this visit can become an office visit.
- e Medical history to include investigator review of immunization status with patient and caregiver.
- f In order to obtain accurate measurements, length should be measured using an infantometer and height should be measured using a stadiometer (WHO Child Growth Standards).
- g Blood pressure measurements should be determined correctly, using the appropriate-sized cuff for the child's age and with the child seated and relaxed.

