#### Patient Characteristics

- [2] Are at least 1 to <18 years of age.
- [3] Are  $\geq 16$  lbs. (7.3 kg).
- [4] Have been treated with only one of the following rapid-acting insulin analogs as part of an MDI regimen for at least the last 90 days:
  - a. insulin lispro U-100, or
  - b. insulin aspart
  - c. insulin glulisine or
  - d. Fast acting insulin aspart (must be approved for use in children in accordance with the local product label)
- [5] Have been treated with only 1 of the following basal insulins for at least the last 90 days:
  - a. insulin glargine U-100 (QD or BID), or
  - b. insulin detemir U-100 (QD or BID), or
  - c. insulin degludec U-100 (QD)
- [6] Use a total daily dose of insulin 0.3 to  $\leq 1.9$  U/kg.
  - a. TDD can be the average of previous 3 to 7 days
- [7] Have a HbA1c value  $\leq 9.9\%$  according to the central laboratory.
- [8] Male patients:
  - a. no male contraception required, except in compliance with specific local government regulations
- [9] Female patients of childbearing potential:

- a. Post pubertal females of childbearing potential are defined as children and adolescents  $\geq 12$  years of age or  $< 12$  years of age who have onset of menses.
- b. if sexually active, must agree to use 1 highly effective form of contraception for the entirety of the study ([Appendix 6](#))
- c. not pregnant or intending to become pregnant
  - i. post pubertal females of childbearing potential must test negative for pregnancy prior to initiation of treatment as indicated by a negative serum pregnancy test at the screening visit followed by a negative urine pregnancy test within 24 hours prior to exposure to investigational product (IP) at Visit 4
- d. not breastfeeding

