### **10.3.7. Other Analyses**

#### **10.3.7.1. Subgroup Analyses**

The following subgroups will be analyzed using the efficacy estimand to evaluate consistency of treatment effects on the primary efficacy measure if there are sufficient numbers of patients in each treatment by subgroup (for example, 10%):

- Age (Age Group 1: 1 to <12, 12 to <18 years and Age Group 2: 1 to <6, 6 to <12, 12 to <18 years)
- HbA1c stratum ( $\leq 8.0\%$ ,  $> 8.0\%$ )
- Type of basal insulin at randomization (insulin glargine, detemir, or degludec)
- Sex (male or female)
- BMI ( $< 25$ ,  $\geq 25$  kg/m^2 and  $< 30$ ,  $\geq 30$  kg/m^2)
- Duration of diabetes (using the median as the cutoff)
- Race
- Ethnicity
- Country
- Region
- Prandial insulin dosing plan (carbohydrate counting, pattern adjustment).

Analyses for HbA1c and change from baseline in HbA1c will be performed using an MMRM model that includes the same fixed effects given for the primary analysis model plus factors of subgroup, 2-way interaction of subgroup and treatment, 2-way interaction of subgroup and visit, and 3-way interaction of treatment, visit, and subgroup. The interaction of subgroup and treatment at the primary endpoint (Week 26) will be evaluated to assess the treatment by subgroup interaction.

Additional subgroup analyses may also be performed.

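### The BMI subgroup uses fixed cut-offs of 25 and 30 kg/m² for all ages from 1 to <18, so it tests consistency by BMI poorly in younger children and is partly confounded with age

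*SAP*

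**What the plan says.** SAP 5.13.1 lists the BMI subgroup for HbA1c as "Body Mass Index (BMI, < 25 kg/m², ≥ 25 kg/m² and < 30 kg/m², ≥ 30 kg/m²". Protocol 10.3.7.1 gives the same three bands. The age criterion in Protocol 6.1 is "Are at least 1 to <18 years of age". Neither document gives a BMI percentile, z-score or age-specific cut-off. The growth standard in the Schedule of Activities is cited only for how length and height are measured ("height should be measured using a stadiometer (WHO Child Growth Standards").

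The stated purpose in Protocol 10.3.7.1 is "to evaluate consistency of treatment effects on the primary efficacy measure". Both documents attach a size condition, given as an example and worded differently. The SAP has "at least 10% in each group" and the protocol has "in each treatment by subgroup (for example, 10" percent. Neither says what happens when one band of a subgroup falls short.

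Under SAP 5.13.1 the ITT analysis adds subgroup and subgroup-by-treatment to the primary ANCOVA. The efficacy-estimand analysis adds these terms and their visit interactions to the primary MMRM. Age group (1 to <12, 12 to <18) enters both primary models as a main effect only (SAP 5.11.1). On the test level, SAP 5.13.1 says: "The subgroup interaction effect will be evaluated using a significance level of 0.10, unadjusted".

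**The concern.** BMI changes with growth, so a value of 25 kg/m² does not mark the same relative body size in a young child as in a 17-year-old. With one cut-off for every age, the upper bands are likely to draw mostly on adolescents, and a young child with high BMI for age is likely to be placed with the lean children.

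Two things are at stake in interpreting this subgroup. A treatment effect that depends on relative BMI in younger children would be hard to see. And because the model lets the treatment effect vary by BMI band but not by age, a difference in effect between age groups can surface as a BMI interaction.

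**Working it through.** **Design figures.** The documents give no figure for the BMI subgroup. The inputs borrowed from Protocol 10.1 (SD 1.1, 240 completers per blinded arm, 15% dropout) do reproduce its own figures:
- NIM 0.4: Φ(0.4/(1.1·√(2/240)) − 1.96) = 97.8% (stated >95%).
- NIM 0.3: 84.8% (stated >80%).
- LY900014+20, 240 vs 120, distance to margin 0.4 − 0.07 = 0.33: 76.5% (stated about 76%).
- 240/0.85 → 283 and 120/0.85 → 142, so 283 + 283 + 142 = 708.

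**What the cut-off means at small heights.** Weight = BMI × height². At assumed heights of 86, 115 and 138 cm, 25 kg/m² needs 25 × 0.86² = 18.5 kg, 25 × 1.15² = 33.1 kg and 25 × 1.38² = 47.6 kg. For 30 kg/m² the weights are 22.2, 39.7 and 57.1 kg.

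**Age mix of the bands (assumed ranges).** Let f be the share under 12 (30-50%), and let the probability of BMI ≥25 rise in step from 1% to 10% under 12 and from 15% to 30% at 12 or over. Adolescent share of the ≥25 group = (1 − f)·p(12+) / [f·p(<12) + (1 − f)·p(12+)].
- f = 0.3, 1% and 15%: 0.105/0.108 = 97%.
- f = 0.5, 10% and 30%: 0.15/0.20 = 75%.

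Over the range, adolescents are 75-97% of the ≥25 group and 44-67% of the <25 group. The ≥25 group is 8-24% of patients.

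**Illustrative simulation.** Assumptions: 30% or 45% under 12; ages uniform over 4 to 12 and 12 to 18; median BMI 15.5-16 below age 6, rising linearly to 20-22 at 18; log-SD 0.12-0.16.
- The ≥25 group is 91-99% adolescent.
- It captures 0-9% of under-12s in the top 15% of BMI for age, against 8-71% of such adolescents.
- It holds about 1-8% of patients, and the ≥30 group under 1%.

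**Size condition.** 10% of 708 is 70.8 patients. On the protocol's treatment-by-subgroup wording it is 28.3 per blinded arm and 14.2 in the open-label arm. The ≥30 group fails in every simulated setting. The whole ≥25 group fails there too, but passes in most of the wider grid.

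**Confounding with age.** Suppose the treatment effect differs by 0.3 between the two age bands and does not depend on BMI. With randomized treatment and age as a main effect only, and the upper bands combined, the expected BMI-by-treatment coefficient is 0.3 × (adolescent share of ≥25 − adolescent share of <25).
- Smallest in the grid: 0.3 × (0.875 − 0.645) = 0.07.
- Largest: 0.3 × (0.938 − 0.462) = 0.14.

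The same formula on the simulated shares gives 0.08-0.13. Single simulated fits ranged from 0.02 to 0.14; the spread beyond 0.08-0.13 is sampling noise in a small ≥25 group.

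**Precision.** For two BMI groups, SE = 1.1·√(2/n₁ + 2/n₀), tested two-sided at 0.10.
- 10% at ≥25 (24 and 216 per arm): SE = 1.1·√(2/24 + 2/216) = 0.33; power for a 0.4-point interaction is 33%.
- 20% (48 and 192 per arm): SE 0.25, power 48%.

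**The case against.** The strongest reply is that the fixed cut-offs do carry BMI information. In the simulation 93-100% of patients at ≥25 were in the top 15% of BMI for their age, and membership correlated more with BMI for age (0.21-0.51) than with age (0.08-0.23). Age group is adjusted for as a main effect, and age has its own subgroup analysis in two groupings. The analysis is supportive and unadjusted, and SAP 5.13.1 allows further subgroup analyses. All of this stands.

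It also rules out several stronger readings that a reader might infer:
- That the subgroup sorts patients largely by age, or that nearly everyone at ≥25 is an older adolescent. The documents give no age or BMI distribution, and the correlations above point the other way on the first part.
- That it cannot test consistency by BMI. Among adolescents the cut-offs still separate high from lower relative BMI.
- That it merely repeats the age analysis. At most about half of the assumed age difference leaks into the BMI term (0.14 of 0.3).
- That the 10% condition will remove the upper bands. It is only an example, and the ≥25 share is unknown.
- That the stated target is adiposity. The protocol speaks only of consistency of treatment effects.

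What the reply does not answer is the insensitivity under age 12, the missing age-by-treatment term, and the lack of a rule for sparse bands.

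**Conclusion.** The point holds as a cheap improvement to a supportive analysis. Both documents apply unstandardized cut-offs to ages 1 to <18, and the subgroup models cannot fully separate a BMI interaction from an age interaction. Under the assumed ranges the ≥25 group is about 75-99% adolescent, 91-100% of under-12s with high BMI for age fall below 25, and the ≥30 group may miss the size condition. An age-only effect difference of 0.3 would produce an apparent BMI interaction of about 0.07-0.14. That is well below its standard error of 0.25-0.33, so it would rarely decide the test alone, but it would blur the estimate. These figures rest on assumed age and BMI distributions; only the cut-offs, the model terms and the absence of a merging rule come from the documents. The primary and gated HbA1c tests are unaffected.

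**What to change.** In SAP 5.13.1, define the BMI subgroup by age- and sex-standardized BMI, in z-score or percentile bands, from baseline (Visit 4) height and weight. Name one growth reference that covers 1 to <18 years. State before unblinding that a band below the size condition is merged with the adjacent band, and whether the condition applies overall or within each treatment arm. If the reference fits the trial population, the bands will have a similar age mix, which removes most of the confounding without another model term.

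The cost is SAP wording and one derived variable; age, sex, height and weight are already collected. Protocol 10.3.1 lets a change that is not a principal feature be described in the SAP or study report, so no protocol amendment is needed. The downside is loss of direct comparability with analyses that use 25 and 30 kg/m². Keeping those cut-offs as an additional analysis in patients aged 12 to <18 would preserve it where they are most informative.

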5.13.2. Subgroup Analyses for Hypoglycemic Events

For the documented hypoglycemia based on the threshold of BG ≤ 70 mg/dL, the following subgroups will be analyzed:

- age (age group 1: 1 to <12 years and 12 to <18 years, and age group 2: 1 to <6, 6 to <12, and 12 to <18 years)
- hemoglobin A1c stratum ($\leq 8.0\%$ versus $>8.0\%$)
- region
- type of basal insulin (glargine, degludec, and detemir)
- prandial insulin dosing plan (carbohydrate counting or pattern adjustment)
- personal CGM/FGM use (yes, no)

The event rate and incidence will be analyzed using the same model specified in [Table ITSB.5.4](#) with the addition of factors for subgroup, and 2-way interaction of subgroup and treatment. The 2-way interaction will be used to evaluate treatment-by-subgroup interaction.

5.14. Interim Analyses and Data Monitoring

No interim analyses are planned for this study. If an unplanned interim analysis is deemed necessary, the appropriate Lilly medical director, or designee, will be consulted to determine whether it is necessary to amend the protocol.

A data and safety monitoring committee (DMC) consisting of pediatric experienced members external to the study team will review interim safety results at least once during the study. The DMC comprises those individuals responsible for the evaluation and interpretation of the results from the safety analysis. The DMC for this study will be conducted as an independent DMC. Therefore, the members of the DMC are external to Lilly. Further details pertaining to the DMC activities may be found in the DMC charter. Only safety analyses will be conducted for DMC review, no efficacy analysis will be conducted. The analyses for DMC will neither be reported to study team nor change the study design.

5.15. Clinical Trial Registry Analyses

Additional analyses will be performed for the purpose of fulfilling the Clinical Trial Registry (CTR) requirements.

Analyses provided for the CTR requirements include the following:

- Summary of AEs, provided as a dataset that will be converted to an XML file. Both Serious Adverse Events and “Other” Non-Serious Adverse Events are summarized by treatment group, by MedDRA PT.
 - An AE is considered “Serious” whether or not it is a TEAE.
 - An AE is considered in the “Other” category if it is both a TEAE and is not serious. For each Serious AE and “Other” AE, for each term and treatment group, the following are provided:
 - the number of participants at risk of an event
 - the number of participants who experienced each event term
 - the number of events experienced
 - For each SAE, these additional terms are provided for EudraCT:
 - the total number of occurrences causally related to treatment
 - the total number of deaths
 - the total number of deaths causally related to treatment
 - Consistent with www.ClinicalTrials.gov requirements, “Other” AEs that occur in fewer than 5% of patients/subjects in every treatment group may be excluded if a 5% threshold is chosen. Allowable thresholds include 0% (all events), 1%, 2%, 3%, 4%, and 5%.

Adverse event reporting is consistent with other document disclosures (for example, the CSR, manuscripts, and so forth).

6. Unblinding Plan

6.1. Safety Monitoring

An independent DMC will have the responsibility to review the safety results in order to monitor safety of the patients in the study until the last patient completes the treatment period. Members will not have contact with anyone involved in the clinical care of patients and/or enrolled in this study in any way that could compromise the integrity of study. A limited number of preidentified individuals external to the study team will perform the data analysis for the DMC using the limited unblinded data. The detailed analysis and communication plan for the analyses will be defined in a separate DMC charter.

6.2. Site Level Unblinding

Investigators, patients, and study site personnel will be blinded to the double-blind treatment groups throughout the study. Investigators, patients, and study site personnel will be unblinded to the open-label treatment group.

The following applies to the double-blind treatment groups:

Emergency unblinding for AEs may be performed through the IWRS. This option may be used ONLY if the patient's well-being requires knowledge of the patient's treatment assignment. All calls/website visits resulting in an unblinding event are recorded and reported by the IWRS.

The investigator should make every effort to contact the Lilly clinical research physician or designee prior to unblinding a patient's treatment assignment. If a patient's treatment assignment is unblinded, Lilly must be notified immediately.

If an investigator, site personnel performing assessments, or patient is unblinded during the double-blinded period, the patient must discontinue the IP and will be encouraged to continue in the study (Protocol Section 8.1).

Appendix 1. Empirical Estimation of Relative Event Rate

Traditionally, Poisson distribution has been assumed to draw inference for the rate of rare events. When the event is rare and the sample size is large, it is known that the overall number of events is approximately from Poisson distribution. However, for some not very rare events such as severe hypoglycemic events in T1D patients, the total number of events may not be distributed from Poisson and may be over-dispersed. Assuming Poisson distribution may significantly underestimate the variance, and therefore traditional method may reduce the coverage probability and inflate the Type-I error. An empirical method in estimating the variance of the relative event rate without assuming any distribution on the number of events will be provided in this appendix.

Let X_{ij} denote the count response variable for patient j in treatment group i . Let $Y_i = \sum_j X_{ij}$ be the total number of events for treatment group i , and T_i denote the exposure for treatment group i . Let $i = 0$ for the control group and $i = 1$ for the experimental treatment group. The event rate for treatment group i can be calculated as:

$$\hat{r}_i = \frac{Y_i}{T_i}$$

The empirical variance of \hat{r}_i is

$$\widehat{Var}(\hat{r}_i) = T_i^{-2} \widehat{Var}(Y_i) = T_i^{-2} n_i S_i^2,$$

where S_i^2 is the variance of X_{ij} for treatment group i . Using the delta-method, the variance of $\log(\hat{r}_i)$ can be estimated as

$$\widehat{Var}(\log(\hat{r}_i)) = Y_i^{-2} n_i S_i^2$$

The relative rate of the experimental treatment versus the control treatment is estimated as

$$\hat{\lambda} = \frac{\hat{r}_1}{\hat{r}_0}$$

The variances of $\hat{\lambda}$ and $\log(\hat{\lambda})$ are

$$\widehat{Var}(\hat{\lambda}) = \hat{\lambda}^2 \widehat{Var}(\log(\hat{\lambda}))$$

$$\widehat{Var}(\log(\hat{\lambda})) = \widehat{Var}(\log(\hat{r}_0)) + \widehat{Var}(\log(\hat{r}_1)) = Y_0^{-2} n_0 S_0^2 + Y_1^{-2} n_1 S_1^2$$

Assuming $\log(\hat{\lambda})$ is asymptotically from a normal distribution, the $100(1 - \alpha)\%$ confidence interval for $\log(\hat{\lambda})$ can be constructed as

$$\left[\log(\hat{\lambda}) - z_{1-\frac{\alpha}{2}} \sqrt{\widehat{Var}(\log(\hat{\lambda}))}, \log(\hat{\lambda}) + z_{1-\frac{\alpha}{2}} \sqrt{\widehat{Var}(\log(\hat{\lambda}))} \right]$$

Then, the $100(1 - \alpha)\%$ confidence interval for $\hat{\lambda}$ is

$$\left[\hat{\lambda} \exp\left(-z_{1-\frac{\alpha}{2}} \sqrt{\widehat{Var}(\log(\hat{\lambda}))}\right), \hat{\lambda} \exp\left(z_{1-\frac{\alpha}{2}} \sqrt{\widehat{Var}(\log(\hat{\lambda}))}\right) \right] \quad (1)$$

The p-value for testing the null hypothesis of $H_0: \lambda = 1$ is calculated as

$$p = 2\Phi\left(|\log(\hat{\lambda})| / \sqrt{\widehat{Var}(\log(\hat{\lambda}))}\right) \quad (2)$$

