#### **10.3.4. Safety Analyses**

Safety measures will include AEs, hypoglycemia, vital signs and weight, treatment exposure, laboratory measures, and antibodies to insulin lispro. Analyses will be performed on data collected from randomization through Visit 801 for both treatment groups.

Events that are newly reported after the first dose of IP or reported to worsen in severity from baseline will be considered treatment-emergent AEs (TEAEs). The Medical Dictionary for Regulatory Activities (MedDRA) lowest level term (LLT) will be used in the treatment-emergent assessment. The maximum severity for each LLT during the baseline period will be used as baseline severity.

The SAEs, AEs reported as reason for discontinuation from the IP or study, and TEAEs will be summarized in tables using the MedDRA PT, sorted by decreasing frequency within the LY900014 treatment group. The TEAEs will also be summarized by PT sorted by decreasing frequency within SOC for all TEAEs and by maximum severity. For events that are specific to only 1 sex, the denominator and computation of the percentage will include only patients from

the given sex. The number and proportion of patients with at least 1 event for each type of event will be summarized and compared between treatment groups using Fisher's exact test.

Hypoglycemia rates will be summarized for periods of 30 days, 1 year, and 100 years (severe hypoglycemia only). The rate of severe hypoglycemia per 100 years will be compared between treatment groups using the empirical method (details will be described in SAP). For each of the other categories of hypoglycemia, the number of hypoglycemia events during a specific period after randomization (for example, Weeks 0 to 12 of treatment period) will be analyzed by using a negative binomial regression model. The model will include treatment and age group as covariates. An offset defined as the log transformation of treatment exposure in the specific period (days)/365.25 days (or 30 days) will be included in the model to estimate the rate of hypoglycemia per year (or per 30 days). The proportion of patients with at least 1 hypoglycemic event in each category during a specific period after randomization will be analyzed using a logistic regression model including treatment and age group as covariates.

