5.5. Multiple Comparisons/Multiplicity

The test for superiority in HbA1c change from baseline (the second gated objective) will be conducted only when the test for noninferiority (the first gated objective) has been achieved. The gated objectives won't be conducted if the primary objective cannot be met.

No multiplicity test adjustment will be made for other objectives.

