Rate of hypoglycemic events (per patient per year) All Documented ^a Nocturnal ^a Non-Nocturnal (Documented and occurred between waking and bedtime) ^a	0-12, 0-26weeks	Negative binomial regression with treatment and age group as covariates, log (exposure/365.25 days) as the offset in the model.
Incidence of hypoglycemic events All Documented ^a Nocturnal ^a Non-Nocturnal (Documented and occurred between waking and bedtime) ^a	0-12, 0-26weeks	Logistic regression with treatment and age group as covariates.
Rate of post-dose hypoglycemic events (per patient per year) for all 3 main meals All Documented ^a	≤1, ≤2, ≤4, >4, and >2 to ≤4 hours after start of prandial insulin dose within 0-12, 0-26,weeks	Negative binomial regression with treatment and age group as covariates, log (exposure/365.25 days) as the offset in the model.
Incidence of post-dose hypoglycemic events for all 3 main meals All Documented ^a	≤1, ≤2, ≤4, >4, and >2 to ≤4 hours after start of prandial dose within 0-12, 0-26,weeks	Logistic regression with treatment and age group as covariates.
Rate of severe hypoglycemic events (per patient per 100 years)	0-12, 0-26weeks	Exposure adjusted rate 100 years (calculated by total number of events divided by total exposure for individual patients) will be provided and the empirical method (see Appendix 1 for details) will be used for treatment comparison.
Incidence of severe hypoglycemic events	0-12, 0-26weeks	Proportion of patients with severe hypoglycemia will be reported. The treatment comparison will be based on a logistic regression model with treatment and age group as covariates.

^a All documented hypoglycemia and the subcategories based on the thresholds of blood glucose ≤70 mg/dL and blood glucose <54 mg/dL will be analyzed.

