Appendix 2.6. Additional Analyses

The following key efficacy and safety outcomes collected in the main study (not through CGM addendum) will be analyzed using the CGM Population:

- HbA1c at Week 26
- incidence and rate of documented hypoglycemic events from Week 0 to Week 26
- incidence and rate of nocturnal hypoglycemic events from Week 0 to Week 26
- incidence and rate of non-nocturnal hypoglycemic events from Week 0 to Week 26s
- incidence and rate of severe hypoglycemic events from Week 0 to Week 26

- change from baseline in total, basal and prandial insulin dose, and the ratio of prandial and total insulin dose at Week 26

The analysis methods for the above outcomes will be the same as those specified in Section 5.

Proportion of patients who have achieved the guidance (Battelino et al. 2019) recommended CGM targets of glycemic control (see Table APP.2.2) at Week 26 will also be summarized by treatment and analyzed using logistic regression model with treatment, age group and baseline as covariates.

Table APP.2.2. Guidance Recommended CGM Targets of Glycemic Control

Percentage of time with sensor glucose (24-hour)	Guidance Recommendation
target range	
70-180 mg/dL (3.9-10.0 mmol/L, both inclusive)	>70%
hypoglycemia range	
<70 mg/dL (3.9 mmol/L)	<4%
<54 mg/dL (3.0 mmol/L)	<1%
hyperglycemia range	
>180 mg/dL (10.0 mmol/L)	<25%
>250 mg/dL (13.9 mmol/L)	<5%

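### SAP Appendix 1, formula (2), as printed gives p = 2Φ(|z|), which is at least 1 whenever the statistic is defined and contradicts confidence interval (1) whenever that interval excludes 1

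*SAP*

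**What the plan says.** Protocol section 10.3.4 leaves the method for severe events to the SAP: "The rate of severe hypoglycemia per 100 years will be compared between treatment groups using the empirical method (details will be described in SAP"). SAP section 5.12.4.1, Table ITSB.5.4, covers weeks 0-12 and 0-26 and passes the reader on: "the empirical method (see Appendix 1 for details) will be used for treatment comparison".

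Appendix 1 estimates the relative rate λ̂ and gives an empirical variance for its logarithm. It assumes that log λ̂ "is asymptotically from a normal distribution" and builds a confidence interval for the rate ratio, labelled (1). A sentence opening "The p-value for testing the null hypothesis of" λ = 1 then introduces formula (2): "p = 2\Phi\left(|\log(\hat{\lambda})| / \sqrt{\widehat{Var}(\log(\hat{\lambda". The quotation stops just before the closing brackets; nothing else follows in the formula. No minus sign stands before the absolute value, and no 1 is subtracted from. Φ is not defined.

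The method is used again in the CGM addendum. SAP Appendix 2.6 lists "incidence and rate of severe hypoglycemic events from Week 0 to Week 26" and adds: "The analysis methods for the above outcomes will be the same as those specified in Section 5".

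**The concern.** A two-sided p-value must lie between 0 and 1 and fall as the evidence against the null hypothesis grows. Formula (2) does neither. The absolute value makes its argument non-negative, so twice the normal distribution function starts at 1 and climbs towards 2. Interval (1), printed just above it, uses the same estimate, variance and normal approximation, so the two should agree on whether λ = 1 is rejected. As printed they cannot.

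The stake is limited but real. Formula (2) is the only p-value rule given for the rate comparison in objective 6, a secondary safety objective in children, and neither document corrects it elsewhere. If it is programmed as printed, the output shows impossible p-values beside intervals that may exclude 1. If it is repaired silently in code, the reported analysis departs from the written plan.

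**Working it through.** The documents give no numerical result for this test, so there is no figure to reproduce. The check evaluates the two formulas as written.

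**Inputs from the documents**
- z = |log λ̂| / SE, where SE² = n0·S0²/Y0² + n1·S1²/Y1² (SAP Appendix 1). Y is the number of events in an arm and S² the variance of the per-patient counts.
- Interval (1): λ̂·exp(±1.96·SE) at the two-sided 0.05 level (SAP Appendix 1 and section 5.1).
- Printed p = 2Φ(z) (SAP Appendix 1, formula 2).
- 283 patients in each double-blind arm (Protocol section 10.1), for illustration only.

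**Step 1: range.** Since z ≥ 0, Φ(z) ≥ 0.5 and 2Φ(z) ≥ 1. The correct two-sided value is 2[1 - Φ(z)], and 2Φ(z) + 2[1 - Φ(z)] = 2. The printed p is therefore always 2 minus the correct p.

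| z | printed 2Φ(z) | correct 2[1 - Φ(z)] |
|---|---|---|
| 0 | 1.000 | 1.000 |
| 1 | 1.683 | 0.317 |
| 1.96 | 1.950 | 0.050 |
| 3 | 1.997 | 0.0027 |

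**Step 2: conflict with interval (1).** The interval excludes 1 exactly when |log λ̂| > 1.96·SE, that is, when z > 1.96. There the printed p exceeds 2 × 0.975 = 1.95, while the correct p is below 0.05.

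**Step 3: worked examples.** The event counts are assumptions, as are equal exposure and one event per affected patient. Then S² = (Y - Y²/283)/282.
- 4 against 14 events: SE² = 0.2473 + 0.0681 = 0.3155, so SE = 0.5617. λ̂ = 14/4 = 3.50 and z = 1.2528/0.5617 = 2.230. Interval (1) is 1.16 to 10.52. Printed p = 1.974; correct p = 0.026.
- 8 against 10 events: SE² = 0.1219 + 0.0968 = 0.2187, so SE = 0.4677. λ̂ = 1.25 and z = 0.2231/0.4677 = 0.477. Interval (1) is 0.50 to 3.13. Printed p = 1.367; correct p = 0.633.

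The printed p is larger in the first example, where the evidence is stronger. At such counts interval (1) is itself only a large-sample approximation.

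**Step 4: simulation.** In 20,000 simulated two-arm datasets with 283 patients per arm and assumed, overdispersed event counts, 170 had an arm with no events and gave no statistic. Of the other 19,830, interval (1) excluded 1 in 10,326, and the printed p was at least 0.05 in all of these. The form 2[1 - Φ(z)] agreed with interval (1) in all 19,830.

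**The case against.** **A sign may have been lost in extraction.** The text was read from PDF by a program. One missing minus sign before the absolute value would turn a correct 2Φ(-|z|) into what is shown, and the plan would then contain no error. This cannot be excluded. Against it, the minus signs in interval (1), in the log-scale interval and in the exponents of the variance formulas all survived. The point therefore concerns the formula as it appears here, and the first action is to look at the source.

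**Φ could denote the upper tail.** The SAP does not define it, and that reading would make formula (2) correct. But interval (1) uses the quantile with subscript 1 - α/2, which is lower-tail notation, and nothing in the appendix supports the other convention. If it was meant, the missing definition is the defect, and the same correction supplies it.

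**The intent is clear and the harm small.** This stands. The hypothesis, variance, normal approximation, two-sided level and interval (1) together fix the decision rule, so the analyst gains no discretion. The error shows itself at first output and cannot produce a false claim of significance. Severe hypoglycemia incidence has its own logistic regression in Table ITSB.5.4. All this argues for a low severity, but not for leaving an unusable formula in the plan.

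**Two stronger readings are not supported.** A reader might infer that every possible dataset yields a p of at least 1. With no events in an arm, log λ̂ and its variance do not exist, so the formula yields no value. The documents give no expected event rate from which to judge how likely that is. A reader might also infer that correcting formula (2) completes Appendix 1. That cannot be assured, because the appendix gives no rule for the zero-event case.

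**Conclusion.** The point holds, as a minor error. Whenever both arms have at least one event, formula (2) as printed returns a value from 1 up to, but not reaching, 2. That value equals 2 minus the correct two-sided p and contradicts interval (1) whenever the interval excludes 1.

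This rests on Φ being the standard normal cumulative distribution function and on the formula being faithfully extracted. Confidence is medium because of the second condition.

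The reach is one p-value per treatment comparison: the severe hypoglycemia rate in objective 6, for weeks 0-12 and 0-26, and its repeat for weeks 0-26 in the CGM population. The rate ratio and interval (1) are unaffected. A reader might infer that the error reaches the trial's main conclusions, but the HbA1c tests do not use Appendix 1. Objective 6 also lies outside the gated sequence; SAP section 5.5 says of such objectives: "No multiplicity test adjustment will be made for other objectives".

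**What to change.** Check formula (2) in the source PDF for a minus sign, or a 1 from which Φ is subtracted, that was lost in extraction. If one is there, no correction is needed. If the formula reads as it does here, replace it with:

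p = 2[1 - Φ(|log λ̂| / √V)], where V is the estimated variance of log λ̂ already defined in Appendix 1 and Φ is the standard normal cumulative distribution function.

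The cost is one corrected formula and one defining clause. Data collection, design and the other analyses do not change.
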